#### 14.3.2.2 Simulation study description

Each of the above described scenarios is investigated based on simulated data over 1000 trials. The following assumptions are made in order to run these simulations:

1. The time to event (PD or death), censoring time and accrual time are all assumed to follow exponential distribution. For all the above scenarios the accrual is assumed to be 8 patients per month.
2. The End of Study is assumed to be at the day of 70th event.

Simulation is performed in the following steps:

##### Step 1:

Based on the assumed distributions of time to event and accrual time, PFS data are simulated for patients in the PDR001 arm and SOC arm (randomization ratio 2:1) sequentially until the required number of events (70 events) is reached.

**Step 2:**

The simulated data is then transformed as the number of patients at risk and number of events in different time intervals for each treatment group similar to historical data. But the total number of interval in the simulation depends on maximum event/censored time.

**Step 3:**

As mathematical closed forms are not tractable, hence, posterior distributions for the log (HR) from Bayesian Cox PH model are computed via MCMC combining the mixture MAP prior obtained from the historical data together with the simulated transformed data.

**Step 4:**

Claim positive result for the Bayesian method if Posterior median HR < 0.7 and Prob (HR>1)< 0.1.

**Step 5:**

Repeat step 1-4 for 1000 trials. Calculate the rate of positive results for both the Bayesian design and the frequentist approach.

**14.3.2.3 Simulation study results**

Table 14-10 shows the operating characteristics for the six scenarios.

Results from Table 14-10 shows that the Bayesian Cox PH model using Mixture prior yields reasonable 1-sided type I error (0.081-0.191) and power (0.7-0.92) under different scenarios in alignment between current and historical data.

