### 10.4.2 Statistical hypothesis, model, and method of analysis

Patients are randomized in 2:1 ratio into either PDR001 arm or control arm. The primary efficacy endpoint, PFS as determined based on the central tumor assessment per RECIST v1.1, will be analyzed by study arm. Assuming proportional hazards for PFS, the following statistical hypothesis will be tested to address the primary efficacy objective:

$$H_{01}: \theta_1 \geq 1 \text{ vs. } H_{A1}: \theta_1 < 1$$

where  $\theta_1$  is the PFS hazard ratio (PDR001 arm vs control arm). The analysis to test this hypothesis will consist of a stratified log-rank test at an overall one-sided 10% level of significance. The stratification factor is disease status (locally advanced recurrent NPC vs. metastatic NPC).

As a supportive analysis, a Bayesian Cox proportional hazard (PH) model (see [Appendix 3](#)) will be used to estimate the hazard ratio for PFS between the two treatment combination arms. The final analysis will be performed when 70 events (progressive disease or death due to any cause) are observed from the study.

An evidence-based prior for the non-parametric, interval-specific hazards of the control arm in the Bayesian Cox PH model is derived using available historical PFS data from the list of the phase II studies (see [Table 1-1](#) and [Appendix 3](#)), using the meta-analytic-predictive (MAP) approach ([Neuenschwander et al 2010](#)) with the assumption of moderate/large between-trial heterogeneity. For more details about the model specification including the prior derivation and its operating characteristics please refer to [Appendix 3](#).

Based on the historical studies, the median PFS for the patients in the control arm is assumed to be 5.5 months (165 days).

The dual-criterion for success based on Bayesian Cox PH model is defined to show a positive result if there is enough evidence that monotherapy PDR001 is superior to the control with respect to the primary PFS endpoint, such that:

- Posterior probability ( $HR > 1$ )  $< 10\%$ , and
- Posterior median  $HR < 0.7$

The posterior median of the HRs along with the associated 95% two-sided credible intervals will be produced for the treatment comparison of PDR001 to the control. In addition, the posterior probability that the true HR lies in the following intervals will be produced:

- Substantial efficacy:  $[0, 0.55)$
- Moderate efficacy:  $[0.55, 0.7)$
- Slight efficacy:  $[0.7, 1)$
- No efficacy:  $[1, \infty)$

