### **10.8 Sample size calculation**

Assuming a 2:1 randomization ratio of PDR001 vs. Comparator, 70 events (PD or death) are to be observed in the randomized Phase II to provide 85% power to detect a 0.55 hazard ratio in terms of PFS (corresponding to a median PFS of 10 months in PDR001 group and 5.5 months in the Comparator group), using a log-rank test at a 1-sided significance level of 0.1.

The final primary analysis of PFS will be done using a Bayesian proportional hazard model when there are at least 70 events observed. Based on the simulation results under different scenarios (see [Appendix 3](#)), 70 events provide reasonable operating characteristics in terms of the probability of obtaining a positive result (as defined in [Section 10.4.2](#)). Using the Bayesian

Cox PH model with mixture MAP prior for the yields reasonable 1-sided type I error (0.081) assuming no efficacy (HR=1) and power (0.92) assuming substantial efficacy (HR=0.55) when current data is in alignment with historical data.

Considering a uniform recruitment time of about 14 months and a 15% drop out rate at 12 months, approximately 114 patients need to be randomized in a 2:1 ratio to the two arms in order to observe 70 events after approximately 6 months follow up (approximately 20 months after FPFV):

- 76 patients to the PDR001 arm
- 38 patients to the control arm

EAST® trial design software v5.4 is used to compute the sample size.

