### Mixture prior

To obtain the mixture prior, 50% weight will be assigned to the MAP component, and 50% weight will be assigned to the weakly informative component to be more on conservative side to handle possible prior data conflict.

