**Table 14-9 Different scenarios of operating characteristics simulations**

Scenario#	Current control aligned with prior?	Efficacy Magnitude	Median PFS, SOC arm (months)	Median PFS, PDR001 arm (months)	True Hazard Ratio
1	Yes	No efficacy	5.5	5.5	1
2	Yes	Substantial	5.5	10.0	0.55
3	Yes	Moderate	5.5	8.2	0.67
4	No	No efficacy	7.5	7.5	1
5	No	Substantial	7.5	13.6	0.55
6	No	Moderate	7.5	12.9	0.67

As shown in the [Table 14-9](#), SOC data are simulated to be aligned with the prior for scenarios 1-3. Different magnitudes of efficacy will be tested in these three scenarios by varying the true hazard ratio. For scenario 1, hazard ratio 1 means that there is no efficacy. The simulation output in this case provides Type I error rate. For the other two scenarios, powers are obtained. Similarly for scenarios 4-6, controlled data not aligned with prior are simulated and scenario 4 is the case with no efficacy where the simulation results provides Type I error rate.

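### Appendix 3 pools the aligned (0.081) and non-aligned (0.191) type I errors as one reasonable range in alignment with history, and 10.8 leaves out the 0.191

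*Protocol*

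**What the plan says.** - **Protocol 10.4.2** makes the primary test a "stratified log-rank test at an overall one-sided 10% level of significance". It calls the Bayesian Cox model supportive. Bayesian success needs a posterior probability of HR > 1 below 10% and a posterior median HR below 0.7.
- **Protocol 10.8** sizes the trial on the log-rank test: "70 events (PD or death) are to be observed in the randomized Phase II to provide 85% power to detect a 0.55 hazard ratio", "using a log-rank test at a 1-sided significance level of 0.1". It then names the Bayesian model as the method for the final primary analysis and reports "reasonable 1-sided type I error (0.081) assuming no efficacy (HR=1) and power (0.92) assuming substantial efficacy (HR=0.55"). The same sentence limits these figures to current data that agree with the historical data. The sentence before it refers to Appendix 3 for the other scenarios.
- **Protocol 14.3.1.1** also calls the Bayesian model primary and rests the declaration of study success on it.
- **Protocol 14.3.1.2.2, Mixture prior** gives the historical (MAP) component and the weakly informative component 50% each, "to be more on conservative side to handle possible prior data conflict".
- **Table 14-9** marks scenarios 1 to 3 as aligned with the prior and 4 to 6 as not aligned. The text below it says that "controlled data not aligned with prior are simulated and scenario 4 is the case with no efficacy".
- **Protocol 14.3.2.3** summarises all of this as "yields reasonable 1-sided type I error (0.081-0.191) and power (0.7-0.92) under different scenarios in alignment between current and historical data".

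**The concern.** The summary sentence gives one error range and attaches it to alignment. The top of that range comes from the only null scenario that is not aligned. A reader who relies on the sentence would conclude that the error stays within acceptable limits when the prior is right, and would not learn what happens when it is wrong. That second case is the main risk of borrowing historical controls.

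The figure matters because the role of the Bayesian rule is unsettled. If it is the success criterion, as 10.8 and 14.3.1.1 have it, a control arm that does two months better than history leads to a false claim of success in about one trial in five. The main design section does not say so.

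**Working it through.** **1. The plan's own design figure.** Inputs from 10.8: HR 0.55, one-sided alpha 0.1, power 85%, 2:1 allocation. The Schoenfeld formula is events = (z₀.₉₀ + z₀.₈₅)² / [(2/3)(1/3)(ln 0.55)²] = (1.2816 + 1.0364)² / (0.2222 × 0.3574) = 5.373 / 0.0794 ≈ 68. With 70 events the power is 0.859. The stated 70 events and 85% reproduce, so one-sided 10% is the level behind the sample size.

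**2. Table 14-10 read against Table 14-9.**

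| Scenario | Aligned? | Control median (months) | True HR | Type I error or power | Estimated HR |
|---|---|---|---|---|---|
| 1 | Yes | 5.5 | 1 | 0.081 | 0.973 |
| 2 | Yes | 5.5 | 0.55 | 0.922 | 0.509 |
| 3 | Yes | 5.5 | 0.67 | 0.727 | 0.629 |
| 4 | No | 7.5 | 1 | 0.191 | 0.894 |
| 5 | No | 7.5 | 0.55 | 0.911 | 0.482 |
| 6 | No | 7.5 | 0.67 (as printed) | 0.728 | 0.586 |

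For the aligned scenarios the type I error is 0.081 and the power 0.727 to 0.922. For the non-aligned scenarios the type I error is 0.191. The power range in 14.3.2.3 holds for the aligned scenarios; the error range does not.

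**3. Is 0.191 simulation noise?** Each scenario has 1000 simulated trials (14.3.2.2).

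- Scenario 4: SE = √(0.191 × 0.809 / 1000) = 0.0124; 95% interval 0.167 to 0.215, which excludes 0.10.
- Scenario 1: SE = √(0.081 × 0.919 / 1000) = 0.0086; 95% interval 0.064 to 0.098.
- Ratios: 0.191 / 0.10 = 1.91 and 0.191 / 0.081 = 2.4.

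**4. What would the same rule do without borrowing?** With 70 events and 2:1 allocation, SE(log HR) ≈ 1/√(70 × 2/9) = 0.2535. The condition on the probability of HR > 1 needs an estimate below exp(−1.2816 × 0.2535) = 0.723, so the 0.7 limit binds. At HR = 1 the success rate is Φ(ln 0.7 / 0.2535) = Φ(−1.407) ≈ 0.080. The excess in scenario 4 therefore comes from the historical prior.

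**5. Direction of the bias.** In scenarios 1 to 5 the estimated HR lies below the true HR, which favours PDR001. Under the scenario 4 null it is 0.894, about 11% low. Scenario 6 is left out because its entries disagree: 7.5 / 12.9 = 0.58, whereas an HR of 0.67 needs a PDR001 median of about 7.5 / 0.67 = 11.2 months.

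**6. Directional check only.** An approximate re-simulation used 1000 trials per scenario, the Table 14-8 means and SDs taken as independent across intervals, 50/50 weights, 114 patients and 15% drop-out at 12 months. For scenario 4 it gave 0.202 with the mixture applied per interval and 0.402 with one joint mixture. For scenario 1 it gave 0.130 and 0.153, so it does not reproduce the printed 0.081; the mixture structure and censoring rate are not stated. The log-rank test gave 0.103 in scenario 1 and 0.101 in scenario 4. Nothing below depends on this run.

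**The case against.** Several points on the other side stand.

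- **A reader might infer that 10.8 presents 8% as the false-positive risk without qualification.** It does not. The sentence carries its alignment condition, 0.081 is correct under it, and Appendix 3 is cross-referenced. The fault is only that 0.191 is left out.
- **A reader might infer that the trial's 10% error rate is broken.** That level belongs to the log-rank test, which the prior does not enter. The inflation reaches the primary conclusion only if the Bayesian rule is primary, and the protocol contradicts itself on that.
- **The wording may be a slip** for different degrees of alignment, since the ranges span all six scenarios and Table 14-10 prints 0.191 openly. Nothing suggests concealment. Correcting the slip would mend the label but would not justify calling 0.191 reasonable.
- **The mixture-prior text promises no error rate.** It calls the 50% weight conservative as a way of handling prior-data conflict and does not claim an error at or below 10%.
- **A 7.5-month control median is a stress case.** Section 2.2 puts TTP/PFS at 5 to 6 months at best. But Table 1-1 lists a regimen with a median TTP of 7.5 months (n=15), so the value is within the protocol's own evidence.
- **A reader might infer that the MAP weight must be lowered.** How much inflation to accept under conflict is a design judgement, and no section requires 10% in every scenario. In another approximate reconstruction, which also failed to reproduce 0.081, a 20% weight still gave about 0.12 in scenario 4.

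**Conclusion.** The concern holds as an error in how the operating characteristics are stated. The 14.3.2.3 sentence is wrong for 0.191, which is the non-aligned null, 1.91 times the 10% level and 2.4 times the aligned error. Section 10.8 is accurate but incomplete, and this matters because 10.8 and 14.3.1.1 give the Bayesian rule primary standing.

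The conclusion rests on the sponsor's printed tables, 1000 trials per scenario, and a normal approximation for the no-borrowing comparison. Only one non-aligned control median was simulated, so 0.191 is not shown to be the worst case.

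The practical effect now is on reporting and on any reuse of the design. SAP 2.2.3 says that the primary efficacy analysis was already reported as not statistically significant, and SAP 2.6.2 plans only Kaplan-Meier summaries of PFS for the final report.

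**What to change.** 1. In 14.3.2.3 and 10.8, state that the one-sided type I error is 0.081 (power 0.727 at HR 0.67 to 0.922 at HR 0.55) when control data agree with the prior, and 0.191 when the control median is 7.5 months, which exceeds 10%.
2. Remove the words *reasonable* and *in alignment* from the pooled range.
3. Report any positive Bayesian result with both error rates and with the bias of the estimated HR towards PDR001 (0.894 when the true HR is 1 in scenario 4).
4. Do not change the MAP weight or the posterior thresholds as the decision rule. Enrolment is complete and the primary result is known, so such a change would be post hoc. A lower MAP weight may be shown only as a labelled sensitivity analysis.

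Items 1 and 2 need two sentences rewritten and no new data. The cost is that the stated operating characteristics look less favourable.

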**Table 14-10 Operating characteristics for the six scenarios**

Scenario	Median PFS SOC Arm (months)	Median PFS PDR001 Arm (months)	HR	Type I error/Power	Estimated HR
1	5.5	5.5	1	0.081	0.973
2	5.5	10.0	0.55	0.922	0.509
3	5.5	8.2	0.67	0.727	0.629
4	7.5	7.5	1	0.191	0.894
5	7.5	13.6	0.55	0.911	0.482
6	7.5	12.9	0.67	0.728	0.586

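### Scenario 6 of the Bayesian operating characteristics prints medians that imply HR 0.58 beside a stated HR of 0.67, and the summary in 14.3.2.3 credits a conflict-scenario type I error to aligned data

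*Protocol*

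**What the plan says.** Protocol Appendix 3 studies six scenarios for the Bayesian Cox model. Table 14-9 lists the sixth as "6 No Moderate 7.5 12.9 0.67": control not aligned with the prior, moderate efficacy, medians 7.5 and 12.9 months, true HR 0.67. Table 14-10 repeats those inputs and adds power and mean estimated HR: "6 7.5 12.9 0.67 0.728 0.586". The aligned scenario with the same stated HR reads "3 5.5 8.2 0.67 0.727 0.629". The other two scenarios with a 7.5-month control read "4 7.5 7.5 1 0.191 0.894" and "5 7.5 13.6 0.55 0.911 0.482".

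Section 14.3.2.2 fixes the survival model: "The time to event (PD or death), censoring time and accrual time are all assumed to follow exponential distribution". The tabulated rates are the frequency of meeting a Bayesian dual criterion, given in Step 4: "Claim positive result for the Bayesian method if Posterior median HR < 0.7 and Prob (HR>1)< 0.1".

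Section 14.3.2.3 sums up by saying that the model with the mixture prior "yields reasonable 1-sided type I error (0.081-0.191) and power (0.7-0.92) under different scenarios in alignment between current and historical data". Section 10.8 relies on this appendix to support 70 events, and there it attaches the alignment condition only to the type I error of 0.081 and the power of 0.92.

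**The concern.** With exponential event times the two medians determine the hazard ratio. One row of the two tables breaks that identity, so a reader cannot tell from the row whether 0.728 is the power at HR 0.67 or at HR 0.58. Scenario 6 is the only moderate-efficacy case in which the current control departs from the historical data, so nothing else in the appendix covers it.

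The summary sentence matters a little more. Borrowing from historical controls is judged mainly by what it does to type I error when the new control arm behaves differently. Read literally, the sentence presents 0.191 as an error rate obtained when current and historical data agree. That blurs the distinction the six scenarios were set up to show.

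**Working it through.** **1. HR from the medians (HR = control median / PDR001 median).**

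| Scenario | Medians (months) | Ratio | Printed HR |
|---|---|---|---|
| 1 | 5.5, 5.5 | 1.00 | 1 |
| 2 | 5.5, 10.0 | 0.550 | 0.55 |
| 3 | 5.5, 8.2 | 0.671 | 0.67 |
| 4 | 7.5, 7.5 | 1.00 | 1 |
| 5 | 7.5, 13.6 | 0.551 | 0.55 |
| 6 | 7.5, 12.9 | **0.581** | 0.67 |

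Five rows reproduce. For scenario 6, HR 0.67 needs 7.5/0.67 = 11.2 months. The gap of 1.7 months is not rounding.

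**2. Which HR does the power of 0.728 fit?** Scenarios 4 and 5 share the 7.5-month control, so I interpolated the probit of the positive rate linearly in log HR.
- Scenario 4: probit(0.191) = -0.874 at ln 1 = 0.
- Scenario 5: probit(0.911) = 1.347 at ln 0.55 = -0.598.
- At HR 0.67: ln = -0.4005, fraction 0.670, probit -0.874 + 0.670 × 2.221 = 0.614, power **0.730**.
- At HR 0.581: ln = -0.542, fraction 0.907, probit 1.141, power **0.873**.

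The stated value is 0.728, with Monte Carlo standard error √(0.728 × 0.272/1000) = 0.014. The method is approximate: applied to scenarios 1 and 2 it gives 0.687 at HR 0.67, against 0.727 printed for scenario 3, a miss of 4 points. The discrepancy at HR 0.581 is 14.5 points.

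**3. Which HR does the estimate of 0.586 fit?** Estimated HR divided by true HR is 0.894 in scenario 4 and 0.482/0.55 = 0.876 in scenario 5. For scenario 6 it is 0.586/0.67 = 0.875, or 0.586/0.581 = 1.008. Only 0.67 shows the downward bias of the other two conflict scenarios.

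**4. Log-rank power is not the yardstick.** With 70 events and 2:1 allocation, power = Φ(√(70 × 2/9) × |ln HR| - 1.282). This gives 0.859 at HR 0.55, which agrees with the 85% in Section 10.8. It gives 0.617 at 0.67 and 0.804 at 0.581, and 0.728 lies between them. But the same formula also misses scenario 2 (0.859 against 0.922) and scenario 3 (0.617 against 0.727), because the tabulated rates come from the Bayesian rule and prior.

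**5. Re-simulation.** I used the Table 14-8 prior, a 50/50 mixture in each interval, 70 events, 8 patients per month and 1000 trials per setting. Enrolment cap, dropout and risk-set convention were varied because the protocol does not fix them for the simulation.
- HR 0.67: mean estimated HR 0.57 to 0.59, power 0.80 to 0.84.
- HR 0.581: mean estimated HR 0.50 to 0.51, power 0.93 to 0.95.
- Scenario 5, whose inputs agree: power 0.95 to 0.97 against 0.911 printed.

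The estimated HR again points to 0.67. The power levels run 4 to 6 points high in scenario 5, so they cannot be used to test 0.728.

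**6. The ranges in 14.3.2.3, split by alignment as marked in Table 14-9.**

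| Scenarios | Type I error | Power |
|---|---|---|
| Aligned (1 to 3) | 0.081 | 0.727 to 0.922 |
| Not aligned (4 to 6) | 0.191 | 0.728 to 0.911 |

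Against the one-sided 10% level in Section 10.4.2, 0.191/0.10 = 1.9.

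**The case against.** A reader might infer that the power of 0.728 is itself wrong, fitting neither HR. The documents do not support that. It agrees with the interpolated value at 0.67 and is almost the same as scenario 3 at that HR. Nor is it odd that scenario 6 has scenario 3's power with a lower estimated HR: scenarios 2 and 5 behave alike (estimate 0.509 falling to 0.482, power 0.922 and 0.911). The re-simulated 0.80 to 0.84 cannot overturn it either. The censoring rate, any enrolment cap and the level at which the mixture applies are unstated, and the same model overshoots scenario 5.

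A reader might also say that the power range in 14.3.2.3 is misattributed. It is not: its ends correspond to scenarios 3 and 2, both aligned. Only 0.191 is out of place.

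Nor is 0.191 concealed. Table 14-9 marks scenario 4 as not aligned, Table 14-10 prints the figure in that row, and Section 10.8 links alignment to 0.081 only. The sentence may have been meant to say varying degrees of alignment. That stands as an explanation, but the printed text says something else and conflicts with Section 10.8.

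Finally, the consequence is small. Section 10.4.2 makes the stratified log-rank the test and the Bayesian model supportive, although Sections 10.8 and 14.3.1.1 describe the Bayesian model as primary. Enrolment is complete, and SAP Section 2.2.3 says the primary efficacy analysis has been reported. This limits the weight of the point but does not make the row or the sentence correct.

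**Conclusion.** Two errors of record stand, both minor. First, scenario 6 is internally inconsistent in both tables: the printed medians imply HR 0.58, not 0.67. This follows from the protocol's exponential assumption and needs nothing else. The results in that row fit HR 0.67 and not a 12.9-month median (0.728 against about 0.87), so the likeliest explanation is a misprint for about 11.2 months. That inference assumes power is roughly probit-linear in log HR and that bias is similar across the conflict scenarios; only the simulation code can settle it.

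Second, Section 14.3.2.3 as worded attributes a type I error of 0.191 to aligned data, when the aligned figure is 0.081 and 0.191 arises under prior-data conflict. The sample size does not depend on either error.

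**What to change.** 1. Look up the scenario 6 input in the simulation code. If HR 0.67 was simulated, change 12.9 to about 11.2 months in Tables 14-9 and 14-10; no rerun is needed. If 12.9 months was simulated, relabel the HR as 0.58 in both tables and rerun that scenario to recheck 0.728 and 0.586.
2. Reword Section 14.3.2.3 to give the two groups separately: scenarios 1 to 3 (aligned), type I error 0.081 and power 0.727 to 0.922; scenarios 4 to 6 (not aligned), type I error 0.191 and power 0.728 to 0.911, the lower figure subject to step 1. State that 0.191 is the error rate under prior-data conflict and exceeds the one-sided 10% level.

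The cost is one code check, a few corrected lines and at most one rerun of 1000 simulated trials.
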